PD	pharmacodynamic
PID	participant identification number
PK	pharmacokinetic
QD	once daily
QTL	quality tolerance limit
RAS	Renin-angiotensin-system
SAE	serious adverse event
SAF	safety analysis set
SBP	systolic blood pressure
SC	subcutaneous
sGC	soluble guanylate cyclase
SGLT2i	sodium-glucose cotransporter 2 inhibitor
SmPC	summary of product characteristics
SoA	schedule of activities
SOC	System Organ Class
STEMI	ST elevation myocardial infarction
SUSAR	suspected unexpected serious adverse reaction
TIA	transient ischemic attack
UHF	urgent heart failure
ULN	upper limit of normal
UNS	unscheduled
VICTOR	VerICiguaT GlObal Study in Participants With Chronic Heart Failure With Reduced
	Ejection Fraction
VICTORIA	VerICiguaT GlObal Study in Subjects With Heart Failure With Reduced EjectIon
	FrAction
WOCBP	woman/women of childbearing potential
WONCBP	woman/women of nonchildbearing potential

29 NOV 2023 Page: 7 of 44

1. Protocol Summary

1.1 Synopsis

Protocol Title: A Phase 2b open-label clinical study to evaluate the tolerability and safety of a starting dose of 5 mg of Vericiguat in participants with chronic heart failure with reduced ejection fraction

Short Title: Vericiguat 5 mg initiation study

Regulatory Agency Identifier Number(s):

Registry ID

EU CT: 2023-507682-25-00

IND: 116, 743

Envisaged indication:

Chronic heart failure with reduced ejection fraction

Rationale:

The objective of this study is to evaluate the tolerability of a 5 mg starting dose of vericiguat. The aim of this study is to generate evidence to support streamlining the titration regimen steps from 2 to 1 and enable HFrEF patients to achieve the target dose of 10 mg vericiguat daily within 1 titration step.

Objectives, Endpoints:

Objectives	Endpoints
Primary	
To evaluate the tolerability of 5 mg as a starting dose of vericiguat	Treatment tolerability, defined as the completion of the two-week 5 mg dose without discontinuation of study intervention and without moderate to severe symptomatic hypotension between Visit 1 and Visit 2.
Secondary	
To describe safety events of initiation of 5 mg dose	Any AE reported between Visit 1 and Visit 2.
To further evaluate the tolerability of 5 mg as a starting dose of vericiguat	 Absence of AE related to study intervention between Visit 1 and Visit 2. Continuous intake of study intervention between Visit 1 and Visit 2 or restart of
	study intervention after any temporary interruption.

Overall Design Synopsis:

This is multi-center, a single arm, open label study of vericiguat initiation at 5 mg in HFrEF patients with EF <45%. Participants will undergo a screening visit to assess eligibility. Eligible participants must wait a mandatory 2 weeks before returning for Visit 1 in order to be clinically and hemodynamically stable.

At Visit 1, participants will receive vericiguat with directions to take a 5 mg tablet once daily for 2 weeks. Participants will return for Visit 2 after 2 weeks of treatment.

Unscheduled visits may be utilized between Visits 1 and 2 at the discretion of the investigator.

29 NOV 2023 Page: 8 of 44

Number of Participants:

Approximately 120 participants will be screened to achieve at least 100 participants who are assigned to study intervention and complete the treatment period of up to 2 weeks.

[figure not shown]
Study Arms and Duration:

This is a single arm, open label study. The total study duration is approximately 4 weeks, including a 2-week screening period and a 2-week treatment period.

Data Monitoring/Other Committee: Yes

1.2 Schema

Figure 1-1: Schema

A = assignment to study intervention, D = day, EoS = end of study, S= screening, V = visit

29 NOV 2023

1.3 Schedule of Activities (SoA)

Visit Number	Screening	V1	V2 ^b	UNS c	Notes
Study Day, Window	D -14	D1	D14		
Window (Days)	-4 ^a		+4		
Informed consent	X				
Inclusion and exclusion criteria	Х	Х			Recheck clinical status before assignment and/or 1st dose of study intervention.
Demography	X				
Full physical examination including height and weight	X				
Optional: local lab- clinical chemistry, hematology	x				eGFR, albumin, hemoglobin, total bilirubin, ALT and AST values must be available at screening. Values obtained as part of routine management should be used if measured within 30 days prior to Visit 1. If data is unavailable, values should be determined using a local lab.
Serum OR urine pregnancy test (WOCBP only)		Х			If a urine test cannot be confirmed as negative (e.g., an ambiguous result), a serum pregnancy test is required.
Medical history	X				Includes substance usage and family history of premature CV disease
Current status of heart failure medical conditions		Х	Х		Collect any changes to heart failure medical condition (hospitalization, worsening of condition).
Prior and current medications	Х	Х	Х	Х	Assess at any visit including daily dose, time of intake and dosing regimen
Local 12-lead ECG	X				
Vital signs	X	Χ	X	X	Vital signs should be measured before study intervention intake. See Section 8.3.2.
Study Intervention Assignment		Χ			
Intake of Study Intervention		X			Study intervention should be taken orally with food at the same time each day, preferably in the morning. Date and time of study intervention intake will be recorded at Visit 1. Participants must remain at the site for 2 h after intake of first dose of study intervention. Study intervention is self-administered between Visit 1 and Visit 2. See Section 6 for additional details.
Study Intervention Accountability			Х	Х	
AE review		X	х	Х	See Section 8.4.Includes AESI. At Visit 1, the AE review should be conducted before and 2h after dosing. If AE review is suggestive of symptomatic hypotension, date, time, and severity will be recorded and vital signs should be re-assessed post dose.

AE = adverse event, AESI = adverse event of special interest, ALT = alanine transaminase, AST = aspartate aminotransferase, CV = cardiovascular, D = day, ECG = electrocardiogram, UNS = unscheduled, V = visit, WOCBP = women of child-bearing potential

a Screening must be completed 14-18 days before Visit 1.

b Visit 2 is the end of intervention visit.

c For Unscheduled Visits for AE review and reporting, assessments indicated in the SoA are mandatory. All other procedures selected and performed at unscheduled visits are at the discretion of the investigator and as clinically indicated.

29 NOV 2023 Page: 10 of 44

2. Introduction

Chronic HFrEF is a major source of morbidity and mortality. Clinical outcomes for patients with chronic HFrEF remain poor, despite contemporary evidence-based therapies. Therefore, drugs are needed that effectively target disease mechanisms not addressed by current standard therapy.

Vericiguat, a novel soluble sGC stimulator, is approved for the treatment of HFrEF. Decreased NO availability, sGC desensitization to NO, sGC deficiency, and cGMP signaling are potential contributing factors for HF disease progression. Vericiguat works via stimulation of sGC in the critical NO-sGC-cGMP pathway. Vericiguat has a novel mode of action that targets endothelial dysfunction to improve regulation of vascular tone and myocardial function. Pharmacokinetic, pharmacodynamic, safety and efficacy profiles of vericiguat have been well characterized in a series of Phase 1 (29 studies), Phase 2 (3 studies) and Phase 3 (1 study) studies. In the global Phase 3 study, VICTORIA, treatment of 5050 patients with chronic HF with reduced ejection fraction with vericiguat on top of the standard of care resulted in a 10% reduction in the primary outcome of a composite of death from cardiovascular causes or first hospitalization for HF after a median treatment period of 10.8 months (Armstrong et al. 2020).

In VICTORIA, vericiguat was generally safe and well tolerated with low incidence of symptomatic hypotension and syncope, using a titration regimen (a starting dose of 2.5 mg followed by a 2-step up-titration to the target 10 mg dose) guided by symptoms and SBP to mitigate the risk of hypotension. Correlation between vericiguat plasma concentrations and hemodynamic parameters such as heart rate and SBP has been observed following first dose administration but dissipated with repeated dosing. In addition, no meaningful exposure-response relationship was observed for the incidence of symptomatic hypotension or syncope – after first dose and further during the study. This led to the implementation of a symptom-and SBP-guided 2-step titration scheme for vericiguat posology. A detailed description of the chemistry, pharmacology, efficacy, and safety of vericiguat is provided in the investigator's brochure.

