2.3.1 Risk Assessment

The general risks of vericiguat are known. During the VICTORIA study, AEs more frequently reported in the vericiguat group compared to placebo included hypotension, dyspepsia, nausea, dizziness, and headache. Anemia was also more frequently reported in the vericiguat group compared to placebo. Similar results were reported with riociguat, another sGC

29 NOV 2023 Page: 12 of 44

stimulator. Overall, these events are generally nonserious and manageable (Ghofrani et al. 2013a, Ghofrani et al. 2013b).

Pharmacokinetic-pharmacodynamic (PK-PD) analysis of SOCRATES-REDUCED and VICTORIA revealed a small but statistically significant linear relationship between the change in SBP from baseline to 2 hours post dose and the measured vericiguat C_{max} (PH-38550 2020, R-13340 2020) following initiation of vericiguat treatment. However, no statistically significant relationship was observed between C_{max} and changes in SBP from baseline at later visits, suggesting that subsequent titrations to higher doses had minimal hemodynamic effects.

Based on PK-PD modeling of data from SOCRATES-REDUCED, the mean SBP is predicted to decrease from baseline by an additional 2.0 to 2.5 mmHg (i.e., a 4.0 -5.0 mmHg total decrease) when the starting dose is increased from 2.5 mg to 5 mg (i.e. when exposure is doubled) (PH-38545 2015, PH-38550 2020).

The pharmacodynamic effects of vericiguat were evaluated after single and multiple-dose administrations in healthy participants. All tested doses (up to 15 mg) were administered with ad-hoc dosing (without titration). In a pooled analyses across Phase 1 healthy participant studies, the most frequent AEs were headache, dyspepsia and dizziness, consistent with the predicted effects of an sGC stimulator on smooth muscle relaxation and vasodilation (PH-40726 2020). Generally, the incidence of AEs decreased after multiple dosing and when taken with food as directed (for details, see Section 4.3).

Overall, the anticipated risks associated with a starting dose of 5 mg of vericiguat are deemed in line with the established safety profile of the product.

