2.3.3 Overall Benefit: Risk Conclusion

Vericiguat is a new therapeutic option to fulfill the unmet medical need in patients with chronic HFrEF. Based on current clinical evidence, vericiguat provides an important clinical benefit to adult patients with symptomatic chronic HFrEF, and is well tolerated at doses up to 10 mg daily. The currently known risks associated with the mechanism of action are deemed well characterized. With the higher starting dose of 5 mg only a small decrease in blood pressure of about 4.0-5.0 mmHg is expected after administration of the first dose. In order to

29 NOV 2023 Page: 13 of 44

manage potential side effects, participants will be asked to stay at the site for 2 hours after the first dose.

Considering the measures taken to minimize risks to participants in this study and the expected clinical benefit in patients with worsening HF, the benefit/risk assessment is considered positive and the conduct of the planned study in heart failure patients who will not directly benefit from the study intervention is justified.

3. Objectives, Endpoints

Objectives	Endpoints
Primary	
To evaluate the tolerability of 5 mg as a starting dose of vericiguat	Treatment tolerability, defined as the completion of the two-week 5 mg dose without discontinuation of study intervention and without moderate to severe symptomatic hypotension between Visit 1 and Visit 2.
Secondary	
 To describe safety events of initiation of 5 mg dose To further evaluate the tolerability of 5 mg as a starting dose of vericiguat 	 Any AE reported between Visit 1 and Visit 2. Absence of AE related to study intervention between Visit 1 and Visit 2. Continuous intake of study intervention between Visit 1 and Visit 2 or restart of study intervention after any temporary interruption.

4. Study Design

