4.3 Justification for Dose

The study will assess the tolerability of a starting dose of 5 mg vericiguat, once daily. In the initial clinical pharmacology studies in healthy volunteers, 5 mg (and 10 mg) of vericiguat were administered as an initial dose and were well tolerated (Boettcher et al. 2021).

The approved target dose and titration regimen for vericiguat are based on data from the Phase 1 program in healthy volunteers, the Phase 2b study SOCRATES-REDUCED in HFrEF, and the Phase 3 VICTORIA study in HFrEF. The goal of the present study is to provide tolerability and safety evidence to enable starting treatment on dose 5 mg.

29 NOV 2023 Page: 15 of 44

Several stepwise titration schemes were assessed in the Phase 2 SOCRATES-REDUCED trial, with titration guided by clinic-based BP measurements in each scheme. Comparison of NT-proBNP reduction from baseline at 12 weeks across titration schemes demonstrated a clear trend of larger reductions in NT-proBNP in those titrated to higher target vericiguat doses. The greatest reduction occurred in those titrated to a target dose of 10 mg with this target also having an acceptable safety profile. This led to the 2.5 mg to 5.0 mg to 10 mg titration scheme being adopted for the VICTORIA trial. In VICTORIA, up- and down-titration at the study visits was guided by SBP and the presence or absence of symptomatic hypotension. Overall, this titration regimen was well tolerated and a total of 74% of participants reached the 10 mg target by the end of the titration period (73% of those randomized to vericiguat; 75% of those randomized to placebo;); for participants followed for up to one year, 90% reached 10 mg (89% of those randomized to vericiguat; 91% of those randomized to placebo).

Over the course of VICTORIA, the effect of vericiguat on BP was small, with mean SBP generally < 2 mmHg lower in those treated with vericiguat compared to placebo. The main blood pressure effect was observed early after the first 2.5 mg dose of vericiguat (SBP reduction of about 3 mmHg) in participants who received vericiguat compared with placebo. This small vericiguat-induced decrease in BP did not translate into a meaningful exposure-response relationship for the incidence of symptomatic hypotension or syncope – after first dose and during the further study.

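### The SAP keeps unscheduled blood pressures out of its hypotension tables and sorts participants by their highest reading, so these tables could understate low blood pressure

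*Protocol*

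**What the plan says.** **When blood pressure is measured.** Protocol 1.3 lists vital signs at screening, Visit 1, Visit 2 and unscheduled visits, with the note "Vital signs should be measured before study intervention intake". Protocol 8.3.2 refers back to that schedule and adds no timepoint. On the first dosing day, "Participants must remain at the site for 2 h after intake of first dose of study intervention". The adverse event review is repeated at 2 h, but blood pressure is repeated only under a condition: "If AE review is suggestive of symptomatic hypotension, date, time, and severity will be recorded and vital signs should be re-assessed post dose". Footnote c to the schedule adds: "For Unscheduled Visits for AE review and reporting, assessments indicated in the SoA are mandatory". Vital signs are marked in the unscheduled-visit column.

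**How it is tabulated.**
- SAP 4.1 puts unscheduled measurements in listings and bars them from summaries and frequency tables.
- SAP 4.1.2 takes the earliest value when a planned time point after intake has several.
- SAP 4.5.3.2 summarises values and change from baseline by visit, groups participants by their highest SBP and DBP after baseline, and promises a summary of hypotension criteria that it does not define.
- The SAP's Subgroup Analyses repeat the blood pressure tables by heart failure group and by ARNI and SGLT2 inhibitor use.

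**Who still attends Visit 2.** Under Protocol 7.1, a participant with moderate to severe symptomatic hypotension must stop study intervention but remains in the study for Visit 2.

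**The concern.** A table of post-baseline hypotension should draw on the readings most likely to be low. Here those are readings taken because something happened: at an unscheduled adverse-event visit, or after the first dose in a participant with suggestive symptoms. Followed literally, the SAP keeps the first kind out of the table and leaves the second kind undecided. What remains is one planned reading at Visit 2. For participants who stopped because of hypotension, that reading is taken off drug.

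At stake is the descriptive blood pressure evidence in a study meant to support a change of starting dose (Protocol 4.2). A reader of the report could see few or no participants meeting the criteria while lower values sit only in the listings.

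**Working it through.** **Step 1. Scheduled readings.** Baseline is Visit 1 before dosing (SAP 4.1.1). Scheduled post-baseline readings per participant: 1 (Visit 2, before intake). Routine readings at the 2 h review: 0.

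**Step 2. What the rules do.** Let *v* be the Visit 2 reading and *u* a lower off-schedule reading after the first dose, so *u* < *v*.

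| Rule | Value tabulated |
|---|---|
| As written (unscheduled excluded, maximum) | max(*v*) = *v* |
| Unscheduled included, maximum kept | max(*u*, *v*) = *v* |
| Unscheduled included, minimum used | min(*u*, *v*) = *u* |

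The exclusion is what removes *u*. With one reading, maximum and minimum coincide, so the choice of maximum does no harm by itself. It would, however, still hide *u* if the exclusion alone were lifted, so both rules need to change.

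**Step 3. Triggered Visit 1 readings.** SAP 4.1 would list them only, if they are unscheduled. SAP 4.1.2 would use the earliest, if they belong to a planned time point. The SAP does not say which applies. The earliest of several readings need not be the lowest.

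**Step 4. Effect on a proportion.** Let *m* participants meet a criterion at Visit 2 and *k* meet it only off schedule, among *N* in the safety analysis set. The table shows *m*/*N*; all readings give (*m* + *k*)/*N*. The shortfall is *k*/*N*, or 1 percentage point per participant at *N* = 100. With *m* = 0 as an illustration, and exact (Clopper-Pearson) 95% intervals:

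| *k* | Table as written | All readings counted |
|---|---|---|
| 2 | 0/100 (0 to 3.6%) | 2/100 (0.2 to 7.0%) |
| 5 | 0/100 (0 to 3.6%) | 5/100 (1.6 to 11.3%) |

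**Step 5. How many participants might have such readings.** The documents give no rate. Protocol 2.2 reports symptomatic hypotension or syncope in 2.0% on vericiguat over the first 14 days in VICTORIA, at a 2.5 mg start. That is a rough guide and not a ceiling: an unscheduled visit can follow any adverse event, and the Visit 1 trigger needs only suggestive symptoms of any severity. The other rates below are assumptions. The number is Binomial(100, *p*), shown as mean and 2.5 to 97.5 percentiles.

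| *p* | Participants per 100 with an off-schedule reading |
|---|---|
| 2% | 2 (0 to 5) |
| 5% (assumed) | 5 (1 to 10) |
| 10% (assumed) | 10 (5 to 16) |
| 20% (assumed) | 20 (12 to 28) |

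At 2%, the chance of at least one such participant is 1 − 0.98^100 = 0.87. These counts are upper bounds for *k*, because an off-schedule reading need not be low and Visit 2 may be low as well.

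**The case against.** **Little is lost.** Symptomatic hypotension is an adverse event of special interest and is summarised as such (SAP 4.5.2), and every unscheduled reading appears in a listing. Keeping unscheduled data out of by-visit means is ordinary practice, because such readings are selected. This stands for by-visit means and changes. It does not extend to a table whose purpose is to show who met a hypotension criterion. Low pressure that was not reported as symptomatic hypotension would appear in the listings alone.

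**The answer may lie elsewhere.** SAP Section 1 says that table specifications are in a separate document, which may define the criteria and admit these readings. The SAP's reference to a maximum also suggests that its authors had more than one reading in mind. Both points are fair. But the SAP's general exclusion contains no exception, so a specification that admitted these readings would conflict with it.

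**A stronger reading.** A reader might infer that the absence of a routine 2 h blood pressure is itself an error, because Protocol 2.3.3 says "only a small decrease in blood pressure of about 4.0-5.0 mmHg is expected after administration of the first dose" and the study will not describe that fall. The documents do not support this. No passage promises to measure it. Protocol 4.2 centres monitoring on continuation and moderate to severe symptoms, Protocol 8.6 leaves pharmacodynamics out, and Protocol 2.3.3 gives the 2 h stay the purpose of managing side effects. A routine reading remains an option for the sponsor to weigh. With all 100 measured and an assumed SD of change of 10 to 15 mmHg, the 95% CI half-width, t(0.975, 99) × SD/√100, would be 2.0 to 3.0 mmHg. It would need an amendment and would have no control. Taken after the 2 h questioning, it would lengthen the stay by about 14 to 16 minutes (10 minutes of rest, then three readings about 2 minutes apart). It could also prompt discretionary interruptions that count against the primary endpoint.

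**Conclusion.** The point holds as a minor gap in the SAP's descriptive safety tables. Unscheduled-visit readings are excluded by the text as it stands; whether triggered Visit 1 readings are excluded is open. The understatement is 1 percentage point per 100 for each participant whose only low reading is off schedule. The total cannot be predicted from the documents and may be zero. This conclusion assumes that the separate table specifications follow the SAP's general rule.

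A reader might also infer that the tolerability result is at risk. It is not: the primary endpoint rests on discontinuation and investigator-assessed symptomatic hypotension (Protocol 9.3.2.1, SAP 4.2.1) and contains no blood pressure threshold.

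**What to change.** Amend SAP 4.5.3.2, before database release:

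1. As a stated exception to SAP 4.1, count every reading after the first dose, including symptom-triggered Visit 1 and unscheduled readings, toward the hypotension-criteria summary. State that the earliest-value rule of SAP 4.1.2 does not apply to this summary.
2. Categorise participants by minimum post-baseline SBP and DBP, in addition to or instead of the maximum, and carry this into the subgroup blood pressure tables.
3. Keep by-visit values and change from baseline on scheduled readings only.
4. Flag Visit 2 readings taken after permanent discontinuation of study intervention.

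The cost is a revised SAP version and some programming. No new data or protocol amendment is needed, and the change remains possible after enrolment has closed. The price is in interpretation: extra readings are symptom-selected and participants will have unequal numbers of them, so the minimum should be labelled descriptive and shown with the number of readings per participant.

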2.1 Study Rationale

The objective of this study is to evaluate the tolerability of a 5 mg starting dose of vericiguat in HFrEF patients; the aim of the study is to generate evidence to support streamlining the titration regimen from 2 steps to 1 step and enable HFrEF patients to achieve the target maintenance dose of 10 mg vericiguat daily.

